#### Results

We screened 123 participants examined in the dental chair to check if they met the inclusion and exclusion criteria (Figure 1). The bleaching procedures were implemented exactly as planned and no modification was performed.

Characteristics of included participants: The baseline color of the volunteers was similar (control group: 5.9 [1.9]; dexamethasone: 5.6 [2.1]); the mean age (SD) between volunteers was similar between the groups (control: 22.5 [2.1] and dexamethasone: 22.3 [2.7]), ranging from 19 to 29 years. Thirty-four percent of the volunteers from the control group, and 23% of the volunteers from the dexamethasone group were men.

*Protocol adherence and dropouts*: No discontinuity in both treatment groups was found in the clinical investigation. All volunteers attended the recall visit 1 week postbleaching.

*Tooth Sensitivity*: Two volunteers, 1 from each group, took an analgesic to alleviate the bleaching-induced TS (Tylenol, Janssen Cilag Farmacêutica) in the period from 5 to 7 hours after the 2nd and last clinical bleachings.

Table 2 shows the number of participants who experienced TS during the bleaching regimen in the control group and dexamethasone group. In this table, it is shown that no significant difference was observed between groups (p = 0.075). The relative risk, along with the 95% confidence interval, is also evidence that the use of the experimental drug protocol had no effect on the reduction of TS.

Tables 3 and 4 show that the TS was similar in both groups, at different assessment points, in both sessions, using both pain scales. It is also seen that the bleaching-induced TS did not last longer than 48 hours after the bleaching protocol (Tables 3 and 4).

Color Evaluation: Significant whitening was observed in both groups (P < .001). The descriptive data from bleaching obtained after the 1st and 2nd bleaching sessions can be seen in Table 5. At the end of the bleaching protocol, a whitening of approximately 3 shade guide units was detected for both groups.

The results of the subjective shade evaluation (VITA Classical: P = 0.27; VITA Bleachedguide 3D-MASTER: P = 0.68) matched the hypothesis of equality between the groups after bleaching. The effect size and the confidence interval for the overall mean difference is also shown in Table 5 and is evidence of no statistical difference between groups.

Adverse effects: In this study, no reports of adverse effects by volunteers were received.

TABLE 1

PRODUCT	INGREDIENTS
Pola Office + SDI*	• 37.5% hydrogen peroxide
	
 
potassium nitrate
 

Soothe SDI*	• potassium nitrate 6.0%
	• fluoride ions 0.10%
	• water 89.60%
	• thickener 4.20%
	• sodium benzoate 0.10%
Dexamethasone capsules**	
 
dexamethasone base 8mg
 

•	• starch 50%
	
 
lactose monohydrate 35%
 

	
 
dibasic calcium phosphate 14%
 

	• magnesium stearate 1%
Placebo capsules**	• starch 50%
	
 
lactose monohydrate 35%
 

	
 
dibasic calcium phosphate 14%
 

	• magnesium stearate 1%
Placebo gel**	• carbopol

\* SDI, Victoria, Australia

\*\* Handled by Bem Viver laboratory Ltda, registration number 09047030/0001-28, located at [name]. Batch of the product: 189155.

# TABLE 2

Participants who exp	erienced too	th sensitivity d	uring the bleaching regi	men in the control group	
and dexamethasone g	group*				
TREATMENT	TOOTH SENSITIVITY (N°. OF PARTICIPANTS)		ABSOLUTE RISK	RISK RATIO (95% CONFIDENCE	
	Yes	No		INTERVAL)	
Control	33	2	0.94	0.24 (0.05 1.26)	
Dexamethasone	28	7	0.80	0.24 (0.05 – 1.26)	
* Fischer's exact test	(p=0.075).				

TABLE 3

Medians and interquartile (1 and 3 interquartile) ranges of the tooth sensitivity at different assessment points using the numeric rating scale (NRS).

ACCECCMENT		First Session		Second Session			
ASSESSMENT TIMES	Control	Dexamethason e	Compariso n group	Control	Dexamethason e	Comparison group	
During bleaching	$0(0-1)^{A}$	0 (0-1) A	NS †	0 (0-1) A	0 (0-1) A	NS	
Up to 1h after bleaching	0 (0-1) A	0 (0-1) A	NS	0 (0-1) A	1 (0-1) A	NS	
Up to 24h after bleaching	0 (0-1) A	0 (0-1) A	NS	0 (0-2) A	0 (0-1) A	NS	
Up to 48h after bleaching	0 (0-0) B	0 (0-0) B	NS	0 (0-0) B	0 (0-0) B	NS	

\* Within each column, significant differences are represented by different uppercase letters.

† NS: No significant difference between groups.

TABLE 4

 $Means \ (standard \ deviations) \ of \ the \ tooth \ sensitivity \ intensity \ at \ the \ different \ assessment \ points \ using \ visual \ analog \ scales.*$ 

A COLECCI MENTE	First Session			Second Session		
ASSESSMENT TIMES	Control	Dexamethasone	Compariso n group	Control	Dexamethason e	Comparison group
During bleaching	8.09 (17.06) AB	7.51 (15.46) A	NS†	14.03 (21.39) A	6.46 (6.34) AB	NS†
Up to 1h after bleaching	11.14 (20.08) A	6.31 (12.78) A	NS	14.31 (20.13) A	7.57 (13.46) A	NS
Up to 24h after bleaching	8.26 (13.48) A	5.06 (9.86) A	NS	16.60 (21.57) A	9.77 (20.55) A	NS
Up to 48h after bleaching	2.91 (9.14) B	0.37 (1.54) B	NS	1.91 (5.46) B	1.14 (4.46) B	NS

\* Within each column, significant differences are represented by different uppercase letters.

† NS: No significant difference between groups.

TABLE 5

Means (standard deviations) of the change in shade guide units obtained with the VITAL Classical\* and VITA Bleachedguide 3D-Master\* at baseline versus each bleaching session and 1 week post-bleaching.

COLOR	GRO	DUPS		MEAN DIFFERENCE
EVALUATION TOOL	Control	Dexamethasone	P VALUE	(95% CONFIDENCE INTERVAL)
VITA Classical	2.14 (1.52)	1.89 (1.37)	0.46	0.35 (-0.43-0.95)
VITA Bleachedguide	1.91 (0.95)	1.86 (0.97)	0.81	0.06 (-0.40-0.52)
VITA Classical	0.74 (1.15)	0.71 (1.49)	0.93	0.03 (-0.61-0.66)
VITA Bleachedguide	1.29 (0.52)	1.23 (0.69)	0.70	0.06 (-0.23-0.35)
VITA Classical	2.54 (2.39)	2.91 (1.96)	0.48	-0.37 (-1.42-0.67)
VITA Bleachedguide	3.00 (1.19)	3.2 (1.35)	0.51	-0.20 (-0.81 -0.41)
VITA Classical	2.77 (1.96)	2.26 (1.87)	0.27	0.51 (-0.40-1.43)
VITA Bleachedguide	3.20 (1.13)	3.09 (1.17)	0.68	0.11 (-0.44 – 0.66)
	VITA Classical VITA Bleachedguide VITA Classical VITA Bleachedguide VITA Classical VITA Bleachedguide VITA Classical VITA Bleachedguide VITA VITA Bleachedguide VITA Classical	COLOR EVALUATION TOOL         Control           VITA Classical         2.14 (1.52)           VITA Bleachedguide         1.91 (0.95)           VITA Classical         0.74 (1.15)           VITA Bleachedguide         1.29 (0.52)           VITA Classical         2.54 (2.39)           VITA Bleachedguide         3.00 (1.19)           VITA Classical         2.77 (1.96)           VITA         3 20 (1.13)	EVALUATION TOOL         Control         Dexamethasone           VITA Classical         2.14 (1.52)         1.89 (1.37)           VITA Bleachedguide         1.91 (0.95)         1.86 (0.97)           VITA Classical         0.74 (1.15)         0.71 (1.49)           VITA Bleachedguide         1.29 (0.52)         1.23 (0.69)           VITA Classical         2.54 (2.39)         2.91 (1.96)           VITA Bleachedguide         3.00 (1.19)         3.2 (1.35)           VITA Classical         2.77 (1.96)         2.26 (1.87)           VITA         3.20 (1.13)         3.09 (1.17)	COLOR EVALUATION TOOL         Control         Dexamethasone         P VALUE           VITA Classical         2.14 (1.52)         1.89 (1.37)         0.46           VITA Bleachedguide         1.91 (0.95)         1.86 (0.97)         0.81           VITA Classical         0.74 (1.15)         0.71 (1.49)         0.93           VITA Bleachedguide         1.29 (0.52)         1.23 (0.69)         0.70           VITA Classical         2.54 (2.39)         2.91 (1.96)         0.48           VITA Bleachedguide         3.00 (1.19)         3.2 (1.35)         0.51           VITA Classical         2.77 (1.96)         2.26 (1.87)         0.27           VITA         3.20 (1.13)         3.09 (1.17)         0.68

\*Manufactured by VITA Zahnfabrik.

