Two calibrated investigators ([name]) independently performed the color evaluations with the shade guide. The 2 examiners, blinded to the allocation assignment, schedule the volunteers for bleaching and evaluated their teeth against the shade guide at baseline and 1 week after the procedure. The 2 examiners were required to have an agreement of at least 85% (Kappa statistic test) before beginning the study evaluation.

Volunteers with anterior restorations or dental prostheses, with anterior orthodontic apparatuses or with severe internal tooth discoloration (tetracycline stains, fluorosis, pulpless teeth) were not included in the study. In addition, pregnant and lactating women, participants with any other pathology that could cause sensitivity (such as gingival recession, dentinal exposure, visible cracks in teeth), those taking anti-inflammatory or analgesic drugs, those who smoked or volunteers who had undergone tooth-whitening procedures were excluded. Those who reported past or present health problems in the stomach, heart, kidneys or liver; those who reported the continuous use of anti-

inflammatory or analgesic drugs; those patients with diabetes, hypertension or the use of antihypertensive drugs; or patients who reported allergies to dexamethasone and lactose were also excluded from the study.

Sample size calculation: The primary outcome of this study was the absolute risk of TS. The absolute risk of TS (that is, the number of patients [percent] who reported pain at some point during dental bleaching) was reported to be approximately 90% for a similar 35% hydrogen peroxide bleaching product [20,21,36]. Thus, a minimum sample size of 70 participants was required to have a 90% chance of detecting, as significant at the 2-sided 5% level, a decrease in the primary outcome measure from 90% in the control group to 60% in the experimental group.

Random sequence generation and allocation concealment: The authors used blocked randomization (block sizes of 2 and 4) with an equal allocation ration, using a 3rd-party service (Sealed Envelope), which did not intervene in the study. Opaque and sealed envelopes containing the identification of the groups were prepared.

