## Statistical analysis

We performed the analysis after the intention-to-treat protocol, and we involved all participants who were randomly assigned [21]. In cases of missing data, the last observation was carried forward. The statistician was masked to the study groups. The absolute risk of TS and its intensity were evaluated by using Fischer's exact test. ( $\alpha = 0.05$ ). The authors calculated the relative risk as the confidence interval for the effect size.

Comparison of the TS intensity (NRS data) of the 2 groups at the 2 different assessment points were performed by using the Mann-Whitney U test, and comparisons between times within each group were performed using the Friedman test. The comparisons of the TS intensity obtained with the VAS scale were evaluated by using a 2-way repeated measures ANOVA and Tukey's test.

Color changes between groups ( $\Delta$ SGU between base line versus 1 week after the 2nd bleaching session) were compared by using a t test, and the shade changes were evaluated by using Student's t test. In all statistical tests, the significance level was 0.05. We performed all analyses by using the software SPSS for windows version 20.0 (IBM).

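### The primary p-value of 0.075 is the one-sided Fisher result; at the planned two-sided level Table 2 gives p = 0.15

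*Combined protocol and SAP*

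**What the plan says.** The Sample size calculation paragraph in Materials and Methods defines the endpoint: "The primary outcome of this study was the absolute risk of TS". The same paragraph sizes the trial to detect a reduction "as significant at the 2-sided 5% level". Randomisation was "with an equal allocation ration".

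The Statistical analysis section names the test: "The absolute risk of TS and its intensity were evaluated by using Fischer's exact test". It adds "In all statistical tests, the significance level was 0.05" but does not repeat whether the tests are one- or two-sided. No section announces or justifies a one-sided test.

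Table 2 gives the counts as "Control 33 2 0.94" and "Dexamethasone 28 7 0.80" (sensitive, not sensitive, absolute risk). The Results text concludes that "no significant difference was observed between groups (p = 0.075"), and the Table 2 footnote gives the same p-value, attributed to Fisher's test.

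**The concern.** A p-value labelled Fisher's exact test should be reproducible from a 2×2 table that is printed in full. This one is reproducible only as a one-sided test, whereas the design is two-sided.

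Three things follow.

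- The printed value is half the value that the planned test gives. At 0.075 the result reads as close to significance; at 0.15 it does not.
- Setting a one-sided p-value against 0.05 allows a nominal 5% false-positive rate in the tested direction, where a two-sided 5% plan allows 2.5%. With these equal arms, any table with a two-sided Fisher p between 0.05 and 0.10 would be declared significant in that direction.
- A reader who takes 0.075 as two-sided, as the design invites, carries the wrong figure forward.

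**Working it through.** **Inputs.** Control: 33 sensitive, 2 not, n = 35. Dexamethasone: 28 sensitive, 7 not, n = 35 (Table 2). There were no dropouts (Results, protocol adherence paragraph), so the table covers all 70 participants. Planned level: two-sided 0.05 (Sample size calculation). Named test: Fisher's exact test (Statistical analysis).

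**Reproducing the printed figure.** Fix the margins: 70 participants, 35 per arm, 2 + 7 = 9 without sensitivity. Let X be the number of those 9 who fall in the control arm. Under the null hypothesis

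P(X = x) = C(35, x) · C(35, 9 − x) / C(70, 9), with C(70, 9) = 65,033,528,560.

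| x | C(35, x) · C(35, 9 − x) | P(X = x) |
|---|---|---|
| 0 | 70,607,460 | 0.00109 |
| 1 | 823,753,700 | 0.01267 |
| 2 (observed) | 4,001,089,400 | 0.06152 |

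The one-sided p-value is P(X ≤ 2) = 0.00109 + 0.01267 + 0.06152 = 0.0753. This is the printed 0.075.

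**The planned two-sided test.** The two-sided Fisher p-value adds every outcome no more probable than the observed one. Because the arms are equal, P(X = x) = P(X = 9 − x), so the opposite tail (x = 7, 8, 9) has the same probability. The remaining outcomes are all more probable than the observed one: 0.163 at x = 3 and 6, and 0.261 at x = 4 and 5. Hence

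p = 2 × 0.07528 = 0.1506.

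**Could another two-sided method have produced 0.075?**

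| Two-sided method | p |
|---|---|
| Likelihood ratio | 0.0671 |
| Wald, risk difference | 0.0676 |
| Pearson chi-square, uncorrected | 0.0742 |
| Linear-by-linear | 0.0763 |
| Barnard | 0.0808 |
| Boschloo | 0.0824 |
| Mid-p (doubled) | 0.0890 |
| Wald, log odds ratio | 0.0924 |
| Chi-square, continuity-corrected | 0.1532 |

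None rounds to 0.075. The nearest, uncorrected chi-square, rounds to 0.074 and is not the test named in the footnote.

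**Is the rest of the inference two-sided?** Two-sided t tests from the Table 5 means and standard deviations, at 35 per arm, give 0.269 (printed 0.27), 0.481 (0.48), 0.513 (0.51) and 0.925 (0.93). The other four rows agree to within 0.02, which rounding of the inputs can explain. The Table 2 interval of 0.05 to 1.26 is a conventional two-sided 95% interval: it reproduces as the Wald interval for the odds ratio, 0.242 (0.047 to 1.263). The primary p-value is thus the exception.

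**The case against.** The arithmetic is not in dispute. The case against concerns how much it matters, and most of it is fair.

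- **No decision depends on it.** Both 0.075 and 0.151 exceed 0.05, and the document claims neither a benefit nor a trend. The corrected value fits its conclusion better. This stands: the overstatement is of the p-value, not of any claim about the drug.
- **The type I error argument is nominal.** Fisher's test is conservative. By exact enumeration at 35 per arm with a common sensitivity rate of 0.87, close to the pooled 61/70 in Table 2, one-sided Fisher at 0.05 rejects 2.1% of the time. At a common rate of 0.90 it rejects 1.6%. Both lie below the 2.5% that the plan allows in that direction. This stands in part. The two-sided test rejects only 0.9% in that direction at 0.87, so the relative inflation is real; and at a common rate of 0.5 the one-sided test reaches 3.6%, above 2.5%.
- **Less conservative two-sided methods also land near 0.075.** Chi-square, Boschloo and mid-p give 0.074 to 0.089. This tempers any claim that the data are far from borderline, but none of these is the named test.
- **It looks like one slip.** The Table 5 p-values are two-sided, and the interval beside the primary p-value includes 1. This too stands: nothing checked suggests a general one-sided policy.
- **The one-sided origin is inferred.** The document does not say how 0.075 was obtained. But if it came from another test, the footnote's label would be wrong and a correction would still be due.

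**Conclusion.** The concern holds. For the named test at the planned sidedness, the primary p-value is 0.151, not 0.075, a factor of exactly 2 because the arms are equal in size. The finding of no significant difference is unchanged.

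This rests on the Table 2 counts being correct and complete, and on reading the two-sided level in the sample size paragraph as governing the primary analysis. That reading is sound: it is the only statement on sidedness in the document, and the other results that can be checked follow it. The point is a necessary correction to the main reported number for the primary outcome. It does not reverse the trial's conclusion.

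**What to change.** 1. In the Results (Tooth Sensitivity paragraph) and in the Table 2 footnote, replace 0.075 with two-sided Fisher's exact p = 0.15 (0.151 to three decimals).
2. In the Statistical analysis section, state that all tests are two-sided at the 0.05 level, so that it agrees with the sample size paragraph.

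Keeping 0.075 and labelling it one-sided would make the number accurate, but it would depart from the stated design and sit beside a two-sided interval, so it is the poorer option.

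The cost is two numbers and one word. No new data are needed, and the interpretation stays the same; the p-value simply becomes less favourable to the experimental arm.

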Study intervention: We divided volunteers into the dexamethasone group, who received the anti-inflammatory (dexamethasone, capsule – 8 mg) and application of a placebo gel, and the control group, who received placebo capsules and the application of desensitizing gel containing 6% potassium nitrate and 0.10% fluoride sodium (Soothe, SDI, Victoria, Australia). All volunteers received the same bleaching treatment, which 4 experienced operators ([name]) performed. One week before the in-office bleaching session, volunteers received individual pots containing 6 capsules in total, with the dexamethasone (Handled by Bem Viver laboratory Ltda), or placebo, in identical capsules depending on their allocation group, which contained the same components of the dexamethasone drug except for the active ingredient (Table 1).

The control group received placebo capsules and the application of desensitizing gel containing 6% potassium nitrate and 0.10% fluoride sodium, and the dexamethasone group received the anti-inflammatory (dexamethasone, capsule - 8mg) and application of a placebo gel. Volunteers were treated in 2 clinical sessions with an interval of 7 days (one week) between them. The protocol for use of the product was as follows: The volunteers in the experimental group received 6 capsules of dexamethasone 8 mg each, which was administered orally, initially 2 days before the 1st bleaching query (8mg, 9 AM, 2 days before the bleaching session; 8mg, 9 AM, 1 day before the bleaching session; 8mg, 9 AM, on the day of the bleaching session) [40]. This same scheme was performed for the 2nd bleaching session, which was 7 days after the 1st. The operators instructed the volunteers to increase adherence to the protocol, and the researches made telephone calls and sent cell phone text messages to remind the volunteers of every capsule to be taken.

Before the dental bleaching, gingival tissue was isolated from teeth using a light-cured resin (Gingival Barrier, SDI), and each tooth was light-cured for 10 seconds using a light curing unit with 1200 mW/cm2 light intensity (Radii-cal, SDI). After the placement of a lip retractor (OptraGate – Ivoclar Vivadent), the operator used the 37.5% hydrogen peroxide gel (polaoffice+, SDI) in three 8-

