minute applications for both groups in accordance with the manufacturer's directions. The bleaching agent was refreshed every 8 minutes during the 24-minute application period. At the end of each session, a single researcher responsible for the blinding [name] delivered a single syringe to the operator, which would contain desensitizing gel if the patient was in the control group, or placebo gel containing only carbopol (no active ingredient) if the patient was in the dexamethasone group. The gel was applied with a brush on the labial surface of the whitened teeth for 2 to 3 minutes as the manufacturer (Soothe SDI Dental Limited) directed. Two bleaching sessions were performed 1 week apart.

TS evaluation: TS was evaluated during bleaching and up to 1 hour, 24 hours and 48 hours postbleaching. The volunteer was asked to indicate the numeric value of the degree of sensitivity for each of the periods above, using a 5-point numeric rating scale (NRS) in which 0= none, 1= mild, 2= moderate, 3= considerable and 4= severe [2,4,5,7,23].

In addition, the volunteers were also instructed to record the pain intensity using the visual analogic scale (VAS) [3,6-9]. This scale is a 100-milimeter horizontal line with scores of 0 and 100 at their ends, in which 0 = no sensitivity and 100 = severe sensitivity. The volunteer had to mark with a vertical line across the horizontal line of the scale the intensity of the TS. Then, the distance in millimeters from the zero ends was measured with the aid of a millimeter ruler.

The data from each bleaching session were evaluated separately and were merged. For this purpose, the worst score or numeric value obtained in both bleaching sessions was considered for statistical purposes and the determination of the overall risk and intensity of TS.

If the volunteer scored 0 (no sensitivity) in all time assessments from both bleaching sessions, this volunteer was considered to be insensitive to the bleaching protocol. In all other circumstances, the volunteers were considered to have sensitivity stemming from the bleaching procedure. This dichotomization allowed us to calculate the absolute risk of TS, which represented the percentage of volunteers who reported TS at least once during treatment. We also calculated the overall TS intensity.

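### The Results read a non-significant comparison with an active gel as evidence that the drug protocol had no effect; 28/35 versus 33/35 does not show that

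*Combined protocol and SAP*

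**What the plan says.** All references are to the Combined protocol and SAP.

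- **Sample size calculation (Materials and Methods).** The primary outcome is the absolute risk of TS. The trial is sized, at the two-sided 5% level, to detect "a decrease in the primary outcome measure from 90% in the control group to 60% in the experimental group". No equivalence or non-inferiority margin is given here or elsewhere.
- **Study intervention.** The dexamethasone group took dexamethasone capsules and had a placebo gel. The comparator is "the control group, who received placebo capsules and the application of desensitizing gel containing 6% potassium nitrate and 0.10% fluoride sodium". No arm received both placebos.
- **TS evaluation.** The outcome is any-time sensitivity over both sessions: "If the volunteer scored 0 (no sensitivity) in all time assessments from both bleaching sessions, this volunteer was considered to be insensitive". Everyone else counts as sensitive.
- **Statistical analysis.** Fisher's exact test is used for absolute risk, and the relative risk is the named effect measure.
- **Results, Tooth Sensitivity, and Table 2.** TS occurred in 33/35 controls and 28/35 dexamethasone participants. The printed p value is 0.075 and the printed risk ratio is 0.24 (0.05 to 1.26). The text first reports no significant difference, then calls the ratio and its interval "evidence that the use of the experimental drug protocol had no effect on the reduction of TS".

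**The concern.** Failing to reject the null is not evidence for the null. To claim no effect, a trial needs a margin set in advance and an interval lying inside it. This trial has no margin, and its point estimate favours dexamethasone.

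The comparator adds a second limit. The any-time outcome is a valid randomised comparison of two whole strategies. Because the control strategy includes an active gel, even a tight interval around zero would show similarity to the gel strategy. It would not show that the drug does nothing. The sentence at issue does not mention the gel.

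At stake is the message on the primary outcome. A reader who takes the sentence at face value leaves with a negative answer about dexamethasone that the trial did not establish. The ratio and p value beside the sentence are also not what their labels say.

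**Working it through.** **Inputs (Table 2).** Dexamethasone 28 of 35, control 33 of 35 with any TS; 2 controls and 7 dexamethasone participants had none. No dropouts are reported.

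**1. Reproducing the printed ratio.**
- Odds ratio = (28 × 2)/(33 × 7) = 56/231 = 0.242.
- SE of the log odds ratio = √(1/28 + 1/7 + 1/33 + 1/2) = 0.842.
- 95% CI = 0.242 × exp(±1.96 × 0.842) = 0.047 to 1.263.

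This matches the printed 0.24 (0.05 to 1.26), so the figure labelled a risk ratio is the odds ratio. Dividing the two absolute risks printed in the same table gives 0.80/0.94 = 0.85, not 0.24.

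**2. Reproducing the printed p value.** With 9 of 70 participants free of TS, the chance that 2 or fewer of them fall in the control arm is the sum over k = 0, 1, 2 of C(35,k)·C(35,9−k)/C(70,9):

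0.0011 + 0.0127 + 0.0615 = 0.0753.

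That is the one-sided Fisher value. The arms are equal in size, so the two-sided value is 2 × 0.0753 = 0.151. The uncorrected chi-square p is 0.074, so the printed 0.075 fits one-sided Fisher. Neither value is below 0.05.

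**3. Risk ratio, the measure the Statistical analysis section names.**
- RR = (28/35)/(33/35) = 0.848.
- SE of log RR = √(1/28 − 1/35 + 1/33 − 1/35) = 0.0942.
- 95% CI = 0.848 × exp(±1.96 × 0.0942) = 0.705 to 1.021.

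**4. Risk difference.** 0.800 − 0.943 = −0.143.
- Wald: SE = √(0.800 × 0.200/35 + 0.943 × 0.057/35) = 0.0782; 95% CI −0.296 to +0.010.
- Newcombe, from Wilson limits of 0.641 to 0.900 (dexamethasone) and 0.814 to 0.984 (control):
  - lower = −0.143 − √[(0.800 − 0.641)² + (0.984 − 0.943)²] = −0.307
  - upper = −0.143 + √[(0.900 − 0.800)² + (0.943 − 0.814)²] = +0.020
- Agresti-Caffo: −0.294 to +0.024. Miettinen-Nurminen: −0.313 to +0.017.

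**5. Is the planned effect inside the interval?** The plan is 90% to 60%: a difference of −30 points, a risk ratio of 60/90 = 0.667, and an odds ratio of (0.6/0.4)/(0.9/0.1) = 0.167.

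| Scale and method | Lower 95% limit | Planned value | Inside? |
|---|---|---|---|
| Risk difference, Newcombe | −30.7 | −30 | yes |
| Risk difference, Miettinen-Nurminen | −31.3 | −30 | yes |
| Risk difference, Wald | −29.6 | −30 | no, just |
| Risk difference, Agresti-Caffo | −29.4 | −30 | no, just |
| Risk ratio, log | 0.705 | 0.667 | no |
| Risk ratio, adjusted log | 0.709 | 0.667 | no |
| Risk ratio, score | 0.673 | 0.667 | no, just |
| Odds ratio, log | 0.047 | 0.167 | yes |

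Every interval includes no difference, and every interval also includes a large reduction: about 29 to 31 points, or a risk ratio near 0.7.

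**The case against.** **The sentence may only be loose wording for non-significance.** It follows directly on a statement of no significant difference, and the colour results close with a similar phrase about no statistical difference. The documents hold no discussion or conclusion, so the final message is unknown. This bears on how serious the point is, but the sentence still asserts no effect.

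**The comparator is disclosed, and the drug protocol can mean the assigned regimen.** Both are fair. Study intervention sets out the gel allocation plainly, and an active comparator is a design choice, not an error. A reader might infer that the absence of a double-placebo arm is a flaw or biases the result. The documents do not support that: the randomised comparison of strategies is sound, and no direction of bias follows. Even on the regimen reading, the interval does not show no effect.

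**The planned effect is not clearly still in play.** A reader might infer that the interval reaches the effect the trial was designed to find. That is not robust. On the risk ratio, the measure the plan names, 0.667 lies outside all three intervals. On the risk difference the answer turns on the method. The point rests only on a sizeable reduction not being excluded.

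**The first-session reading during bleaching is a cleaner drug contrast.** The capsules began "initially 2 days before the 1st bleaching query", and the gel was supplied later ("At the end of each session, a single researcher responsible for the blinding"). This reading therefore appears to precede any gel, although the text does not say exactly when the score was recorded. It is not the primary outcome. Its difference on the visual analogue scale in Table 4 is 7.51 − 8.09 = −0.58 mm (95% CI −8.35 to +7.19, approximate because the data are skewed). It cannot carry a general statement of no effect.

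**Conclusion.** The concern holds as a correction of interpretation and reporting. The data support the statement that no significant difference in any-time TS was shown between the two strategies. They do not support the statement that the drug protocol had no effect. The size is a risk ratio of 0.85 (0.71 to 1.02) and a risk difference of −14.3 points (Newcombe −30.7 to +2.0; Wald −29.6 to +1.0), with two-sided Fisher p = 0.15.

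This rests on the Table 2 counts being correct and on all 35 participants per arm being analysed, as the Results report. It does not depend on the choice of interval method or on which p value is used.

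A reader should not go further and infer that dexamethasone works or that an effect was missed. Every interval includes no difference, and the corrected two-sided p value is larger than the printed one.

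**What to change.** Replace the sentence in the Tooth Sensitivity paragraph of the Results with, for example:

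> No significant difference in any-time TS was shown between dexamethasone capsules plus placebo gel and placebo capsules plus desensitizing gel (28/35 vs 33/35; risk ratio 0.85, 95% CI 0.71 to 1.02, log method; risk difference −14.3 points, Newcombe 95% CI −30.7 to +2.0; two-sided Fisher p = 0.15). This does not show absence of a drug effect, and the comparison is with an active gel, not with placebo alone.

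In the same edit:
- In Table 2, replace 0.24 (0.05 to 1.26) under the risk ratio heading with 0.85 (0.71 to 1.02). If 0.24 is kept as well, label it as the odds ratio.
- In the Results text and Table 2, replace p = 0.075 with the two-sided value, 0.15.

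The cost is one sentence and two corrected figures, all from counts already printed. The primary outcome and the test do not change. A table of TS incidence by assessment window is not needed for this correction and is at most optional. It would add exploratory comparisons without multiplicity control. The precision would also be poor. Table 3, 0 (0-1) with 35 per arm, bounds events during first-session bleaching at about 9 to 17 per arm, and equal counts in that range give 95% limits of about ±20 to ±22 points.
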